2.3 POTENTIAL RISKS AND BENEFITS

2.3.1 KNOWN POTENTIAL RISKS

SERIOUS INFECTIONS

Some patients treated with Humira (adalimumab) are at increased risk for developing serious infections that may lead to hospitalization or death. Most patients who developed these infections were taking concomitant immunosuppressants such as methotrexate or corticosteroids.

Reported infections include:

Active tuberculosis (TB), including reactivation of latent TB. Patients with TB have frequently presented with disseminated or extrapulmonary disease. Study participants will be tested for TB before starting Humira.

Invasive fungal infections, including histoplasmosis, coccidioidomycosis, candidiasis, aspergillosis, blastomycosis, and pneumocystosis. Patients with histoplasmosis or other invasive fungal infections may present with disseminated, rather than localized, disease. Antigen and antibody testing for histoplasmosis may be negative in some patients with active infection. Consider empiric anti-fungal therapy in patients at risk for invasive fungal infections who develop severe systemic illness. Bacterial, viral, and other infections due to opportunistic pathogens, including Legionella and Listeria.

MALIGNANCIES

Lymphoma and other malignancies, some fatal, have been reported in children and adolescent patients treated with TNF blockers, including Humira. Postmarketing cases of hepatosplenic T-cell lymphoma (HSTCL), a rare type of T-cell lymphoma, have been reported in patients treated with TNF blockers, including Humira. These cases have had a very aggressive disease course and have been fatal. The majority of reported TNF blocker cases have occurred in patients with Crohn's disease or ulcerative colitis and the majority were in adolescent and young adult males. Almost all of these patients had received treatment with azathioprine or 6-mercaptopurine concomitantly with a TNF blocker at or prior to diagnosis. It is uncertain whether the occurrence of HSTCL is related to use of a TNF blocker or a TNF blocker in combination with these other immunosuppressants.

HYPERSENSITIVITY

Anaphylaxis and angioneurotic edema have been reported following Humira administration. If a serious allergic reaction occurs, stop Humira and institute appropriate therapy.

HEPATITIS B VIRUS REACTIVATION

Use of TNF blockers, including Humira, may increase the risk of reactivation of hepatitis B virus (HBV) in patients who are chronic carriers. Some cases have been fatal. Study participants will be screened for HBV. Those with prior evidence of HBV infection will not be allowed to participate in this study.

NEUROLOGIC REACTIONS

TNF blockers, including Humira, have been associated with rare cases of new onset or exacerbation of central nervous system and peripheral demyelinating diseases, including multiple sclerosis, optic neuritis, and Guillain-Barré syndrome. Participants with these disorders will be excluded from the study. If any of these disorders develop, Humira will be discontinued.

HEMATOLOGIC REACTIONS

Rare reports of pancytopenia, including aplastic anemia, have been reported with TNF blockers. Medically significant cytopenia has been infrequently reported with Humira.

CONGESTIVE HEART FAILURE

Worsening and new onset congestive heart failure (CHF) has been reported with TNF blockers. Cases of worsening CHF have been observed with Humira. Participants with known CHF will be excluded from the study.

AUTOIMMUNITY

Treatment with Humira may result in the formation of autoantibodies and, rarely, in development of a lupus-like syndrome. Discontinue treatment if symptoms of a lupus-like syndrome develop.

IMMUNIZATIONS

Patients on Humira should not receive live vaccines. Pediatric patients, if possible, should be brought up to date with all immunizations before initiating Humira therapy. Adalimumab is actively transferred across the placenta during the third trimester of pregnancy and may affect immune response in the in utero exposed infant. The safety of administering live or live-attenuated vaccines in infants exposed to Humira in utero is unknown. Risks and benefits should be considered prior to vaccinating (live or live-attenuated) exposed infants.

ADVERSE REACTIONS

The most common adverse reactions in Humira clinical trials (>10%) were: infections (e.g., upper respiratory, sinusitis), injection site reactions, headache, and rash.

Directly relevant to this protocol, two small studies of TNF-inhibition with monoclonal antibody therapy in children and adults with multi-drug resistant FSGS have been reported.

•	•
Event	Frequency (% of patients reporting)
Severe Adverse Events	
Infection with hospitalization	30% (5/17)
Malignancy	0
Death	0
Other Adverse Events	
GI	24% (4/17)

Table 3. FONT trial summary of reported adverse events in 17 treated patients

Approaches to reduce risks associated with study drugs

Due to the frequent and sometimes serious risks associated with the study drug, specific measures have been instituted to minimize these risks and improve the risk:benefit ratio for participants. Based on past experience with the administration of immunosuppressive therapies to patients with FSGS and TR-MCD, the inclusion and exclusion criteria have been selected to enrich for subjects most-likely to benefit from therapy (see Inclusion Criteria) and to avoid those subjects who are less-likely to benefit or more likely to experience treatment-related toxicity (see Exclusion Criteria). Pregnancy status will be monitored throughout the study. In addition, frequent and routine laboratory monitoring will be carried out throughout the study protocol. The Clinical Investigator is responsible for reviewing and acting on adverse events in accordance with section 6.1.7.

2.3.2 POTENTIAL BENEFITS

In previous studies 4 of 17 (24%) of unselected patients with multi-drug resistant FSGS experienced a 50% reduction in proteinuria and preservation of eGFR with the use of TNF-inhibitor with monoclonal antibody therapy over a 16 week period⁵.

3 OBJECTIVES AND PURPOSE

The primary purpose of this Proof of Concept study is to test the hypothesis that TNF inhibition with adalimumab (Humira) in patients with up-regulation of the intra-renal TNF pathway will result in reduction in urinary indicators of TNF pathway activation, specifically urine MCP1/Cr and TIMP1/Cr levels.

Furthermore, this study is proposed to test the hypothesis that FSGS patients with up-regulation of the TNF pathway can be identified through intra-renal gene expression profiling and assay of urine MCP1/Cr and TIMP1/Cr levels by ELISA.

4 STUDY DESIGN AND ENDPOINTS

4.1 DESCRIPTION OF THE STUDY DESIGN

This Proof of Concept, multi-center, open label, clinical trial addresses the treatment of patients with clinically active FSGS or TR-MCD. Up to eight patients with urinary MCP1/Cr and TIMP1/Cr urinary biomarker levels indicating intra-renal tumor necrosis factor (TNF) upregulation will be treated with 8 weeks of adalimumab therapy to assure a minimum evaluable study sample of six patients. The Humira will be dosed based on weight and administered subcutaneously every two weeks for 8 weeks (5 total doses). The urinary biomarkers MCP1/Cr and TIMP1/Cr will be assessed throughout the study. The primary assessment will be of the reduction in target engagement biomarker levels of urinary TIMP1/Cr or MCP1/Cr from baseline to study week 10. Key secondary outcomes include safety measures, serious adverse events, and adverse events.

4.2 ENDPOINTS

4.2.1 PRIMARY ENDPOINT

The change in urine MCP1/Cr and TIMP1/Cr levels from baseline to study week 10, i.e. 2 weeks after the final dose of adalimumab.

4.2.2 SECONDARY ENDPOINTS

- (1) Incidence of serious adverse events, adverse events and abnormal laboratory tests
- (2) Percent change of eGFR from baseline to week 10
- (3) Percent change in UPC from baseline to week 10
- (4) Proportion of participants achieving a nadir UPC less than 1.5 g/g and at least a 40% reduction from baseline at week 10.

4.2.3 EXPLORATORY ENDPOINTS

- (1) Correlation coefficient between intra-renal gene expression of TNF and urinary MCP1/Cr and TIMP1/Cr biomarker levels at baseline
- (2) Time to reduction of urinary MCP1/Cr and TIMP1/Cr biomarkers from baseline
- (3) Change in urinary EGF biomarker levels between baseline and week 10
- (4) Change in Quality of Life score between baseline and week 10.

Endpoint Rationale:

The target engagement biomarkers, urine MCP1/Cr and TIMP1/Cr, will be the primary endpoints of this study as we hypothesize that the levels of this biomarkers at baseline reflect TNF up-regulation in the kidney and after TNF inhibition will reflect target engagement. Neither eGFR nor urinary protein will be a primary endpoint measure. However, we will measure eGFR and urinary protein to provide estimates for future trials

5 STUDY ENROLLMENT AND WITHDRAWAL

5.1 PARTICIPANT INCLUSION CRITERIA

- 1. Kidney biopsy confirmed FSGS or MCD
- 2. For Minimal Change Disease patients only, history of resistance to corticosteroid therapy
- 3. Increased urinary excretion of biomarkers of TNF activation (MCP1/Cr and/ or TIMP1/Cr) at study screening
- 4. eGFR>30 ml/min/1.73 m² at screening
- 5. Urine protein:creatinine ratio ≥1.5 g/g at screening
- 6. Age 6-80 years
- 7. Weight >15kg
- 8. Stable therapy with angiotensin converting enzyme inhibitors, angiotensin receptor blockers, and oral immunosuppression agents for at least 30 days prior to enrollment
- 9. Birth control use in females of child bearing potential
- 10. Informed consent and assent if applicable

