A Proof of Concept, multi-center, open label, clinical trial addressing the treatment of patients with focal segmental glomerulosclerosis (FSGS) or treatment resistant minimal change disease (TR-MCD). Up to 8 patients with intra-renal tumor necrosis factor (TNF) up-regulation will be treated with 8 weeks of adalimumab therapy. The primary assessment will be of the change in target engagement biomarker levels of urinary TIMP1/Cr or MCP1/Cr from baseline to study week 10. Key secondary outcomes include safety measures, serious adverse events, and adverse events.

Objectives:

This study is proposed to test the hypothesis that FSGS and TR-MCD patients with up-regulation of the TNF pathway can be identified through intra-renal gene expression profiling and assay of urine MCP1/Cr and TIMP1/Cr levels by ELISA.

Furthermore, this study will test the hypothesis that TNF inhibition with adalimumab (Humira) in patients with up-regulation of the intra-renal TNF pathway will result in reduction in urinary MCP1/Cr and/or TIMP1/Cr biomarker levels.

Endpoint

Primary Endpoint: The change in urine MCP1/Cr and TIMP1/Cr levels from baseline to study week 10, i.e. 2 weeks after the final dose of adalimumab

Secondary Endpoints

- (1) Incidence of serious adverse events, adverse events and abnormal laboratory tests
- (2) Percent change of eGFR from baseline to week 10
- (3) Percent change in urine protein:creatinine (UPC) from baseline to week 10
- (4) Proportion of participants achieving a nadir UPC less than 1.5 g/g and at least a 40% reduction from baseline at week 10.

Exploratory Endpoints

- (1) Correlation coefficient between intra-renal gene expression of TNF and urinary MCP1/Cr and TIMP1/Cr biomarker levels at baseline
- (2) Time to reduction of urinary MCP1/Cr and TIMP1/Cr biomarkers from baseline
- (3) Change in urinary EGF biomarker levels between baseline and week 10
- (4) Change in Quality of Life score between baseline and week 10.

Population:

Up to eight patients with kidney biopsy confirmed FSGS or TR- MCD, increased urinary excretion of biomarkers of TNF activation (MCP1/Cr and TIMP1/Cr) at study screening, eGFR>30 ml/min/1.73 m² at enrollment, urine protein:creatinine (UPC) ratio ≥1.5 g/g at enrollment, age between

6-80 years, inclusive, and stable therapy with angiotensin converting

enzyme inhibitors, angiotensin receptor blockers, and oral

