A logistic model was fit with the outcome of TNF Z-score >0 to assess the predictive ability of urinary biomarkers individually and combined. Results are shown in Table 1 for the subgroup of participants with eGFR >45. Model 3, which included both biomarkers as predictors had the highest positive predictive value and correct classification. Correctly classified was calculated by assigning those with an estimated probability of disease >= 50% as having disease and then calculating the % that are correctly classified as having and not having disease (true TNF Z-score > vs <= 0) using a patient sample with eGFR > 45 and either FSGS or MCD.

participants with editives								
	Model 1 c-statistic 0.79		Mod	del 2	Mod	el 3		
Patients with eGFR >45			c-statis	tic 0.79	c-statist	tic 0.82		
(n = 49; 13 Events)	PPV 33%		PPV	67%	PPV	75%		
	correctly classified 69%		Correctly cla	assified 78%	Correctly Cla	ssified 82%		
	OR P-value		OR	P-value	OR	P-value		
Log2(uTIMP/Cr)	1.79	0.017			1.54	0.07		
Log2(uMCP/Cr)			2.31	0.008	1.81	0.08		

Table 1: Results of Multivariable Logistic Models of TNF Z-score >0 in NEPTUNE FSGS and MCD participants with eGFR>45

Because both biomarkers contributed to greater predictive accuracy, both will be measured for patient selection into the clinical trial. The coefficients from the multivariable model will be used to calculate the odds of having a TNF Z-score >0 for each person. Odds are then converted to probability and patients with a probability >= 50% of having a positive TNF Z-score would be eligible for enrollment. Mathematically, the following equations will be used to calculate the probabilities for study inclusion:

- 1. Constant + [log2(uTIMP1/Cr) * Coef1] + [log2(uMCP1/Cr) * Coef2] = log Odds
- 2. Exp(log Odds) = Odds
- 3. Probability = Odds / (1 + Odds)

Using the following coefficients and constant from Model 3 in Table 2:

Logistic regression	Number of obs	=	49
	LR chi2(2)	=	13.61
	Prob > chi2	=	0.0011
Log likelihood = -21.542865	Pseudo R2	=	0.2401

tnf_cat	Coef.	Std. Err.	Z	P> z	[95% Conf.	Interval]
logMCPI_uCR_ngmg	.59214	.3381858	1.75	0.080	0706919	1.254972
log2timp1_uCr_ngmg	.4325066	.2401973	1.80	0.072	0382715	.9032848
cons	-1.001269	.5091692	-1.97	0.049	-1.999222	0033157

i.e., $\log Odds = -1.001269 + 0.59214 * \log 2(uTIMP1/Cr) + 0.4325066 * \log 2(uMCP1/Cr)$.

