5.3 STRATEGIES FOR RECRUITMENT AND RETENTION

Patients will be recruited from the active population of patients with FSGS or TR-MCD w at participating sites. TR-MCD is defined as persistent proteinuria despite treatment. Following informed consent and when appropriate, assent, a screening visit will be conducted. Patients with elevated TIMP1/Cr and MCP1/Cr levels and meeting all other eligibility criteria will be scheduled to receive adalimumab every two weeks for 8 weeks (5 total doses). It is anticipated that only 25% of screened patients will be eligible for study participation based on TIMP1/Cr and MCP1/Cr levels. Eight eligible patients will begin study intervention with a goal to have a minimum of 6 patients fully completing the intervention phase and therefore contributing to the final analysis of the primary endpoint after 5 doses of adalimumab over an 8 week period.

Patients will be compensated for study participation to offset costs related to travel to study visits and incidentals.

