## 5. Study Methods

## 5.1 General Study Plan

This study is designed as a proof-of-concept multi-center, open-label single-arm clinical trial addressing the treatment of patients with FSGS or TR-MCD. Eligibility for the study is assessed during a 6-week screening period where bio-samples are used to assess TNF up-regulation and other laboratory and medical history criteria.

Patients are recruited from the active population of patients with FSGS or TR-MCD at participating sites. TR-MCD is defined as persistent proteinuria despite pre-trial immunomodulating treatment. Following informed consent and when appropriate, assent, a screening visit is conducted. Patients with elevated urinary TIMP1/uCr and MCP1/uCr levels and meeting all other eligibility criteria are scheduled to receive adalimumab every two weeks for 8 weeks (5 total doses).

A participant is considered to have completed the study if they complete the study through week 14 or if they withdraw prior to completion of the final study visit. Participants are followed in the study even if study medication is prematurely discontinued unless they withdraw their consent to do so. End of study is constituted by completion of the last visit for the final participant in the study protocol.

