## 5.2 Inclusion-Exclusion Criteria and General Study Population

#### 5.2.1 Participant Inclusion Criteria

- 1. Kidney biopsy confirmed FSGS or MCD
- 2. For Minimal Change Disease patients only, history of resistance to corticosteroid therapy
- 3. Increased urinary excretion of biomarkers of TNF activation (urinary MCP1/uCr and/or urinary TIMP1/uCr) at study screening
- 4. eGFR>30 ml/min/1.73 m^2 at screening
- 5. Urine protein to creatinine ratio ≥1.5 g/g at screening
- 6. Age 6-80 years
- 7. Weight >15kg
- 8. Stable therapy with angiotensin converting enzyme inhibitors, angiotensin receptor blockers, and oral immunosuppression agents for at least 30 days prior to enrollment
- 9. Birth control use in females of child-bearing potential
- 10. Informed consent and assent if applicable

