## 6. Outcomes

## 6.1 Primary Outcome Assessments

Spot urinary biospecimens to assay MCP1 (ng/mL), TIMP1 (ng/mL) and creatinine (mg/mL) are collected with spot urine tests at screening and weeks 0, 2, 8, and 10. Urine creatinine is used to normalize the urinary MCP1 and urinary TIMP1 by calculating the ratio of urinary MCP1 and urinary creatinine and the ratio of urinary TIMP1 and urinary creatinine.

Urinary MCP1 and Urinary TIMP1 are measured by ELISA methods [2]. There are no published reference ranges for the urinary MCP1/uCr nor urinary TIMP1/uCr levels; however, lower values for both biomarkers are associated with less intra-renal TNF activation. [1] Thus, either absolute or relative changes from baseline to post-treatment time points indicate TNF pathway target engagement by adalimumab and support the proof of concept of this trial.

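### The biomarker entry rule is stated in three incompatible ways; only the model-probability rule can be computed, and its written equation disagrees with its own regression output

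*Protocol*

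**What the plan says.** Three forms of the biomarker entry rule stand in the current text.

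- **Either marker.** Protocol 5.1, criterion 3: "Increased urinary excretion of biomarkers of TNF activation (MCP1/Cr and/ or TIMP1/Cr) at study screening". SAP 5.2.1 has the same rule: "Increased urinary excretion of biomarkers of TNF activation (urinary MCP1/uCr and/or urinary TIMP1/uCr) at study screening".
- **Both markers.** Protocol summary, Population entry: "increased urinary excretion of biomarkers of TNF activation (MCP1/Cr and TIMP1/Cr) at study screening". Protocol 5.3 schedules for treatment "Patients with elevated TIMP1/Cr and MCP1/Cr levels and meeting all other eligibility criteria". SAP 5.1 agrees: "Patients with elevated urinary TIMP1/uCr and MCP1/uCr levels and meeting all other eligibility criteria".
- **Model probability.** Protocol 2.2 fits a logistic model with both log2 markers and says "patients with a probability >= 50% of having a positive TNF Z-score would be eligible for enrollment".

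Neither document gives a cut-off for a raised marker, and SAP 6.1 states: "There are no published reference ranges for the urinary MCP1/uCr nor urinary TIMP1/uCr levels". The numbered criterion does not refer to the model, and the SAP never states the 50% rule.

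Within Protocol 2.2, the regression output gives 0.59214 for MCP1 and 0.4325066 for TIMP1. The equation written below it assigns them the other way: "0.59214 * \log 2(uTIMP1/Cr) + 0.4325066 * \log 2(uMCP1/Cr".

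**The concern.** The rule decides who counts as having an up-regulated intra-renal TNF pathway, which is the population named in the primary hypothesis (Protocol 3, SAP 3.1). It also fixes the analysis set, since Protocol 10.2 and SAP 7.2 analyse eligible participants who received a dose. SAP section 10, item 1, drops the hypothesis that such patients can be identified, on the ground that completing screening demonstrates it. That argument needs one defined screening rule.

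As numbered, criterion 3 cannot be applied or audited without a cut-off. The only performance figures in the protocol (positive predictive value 75%, 82% correctly classified) belong to the model at 50%. Nothing is reported for either of the other two rules. With at most 8 treated, one patient admitted under a different rule is at least 1/8 = 12.5% of the sample.

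**Working it through.** **Inputs.** All are from Protocol 2.2: constant -1.001269; coefficients 0.59214 and 0.4325066; log likelihood -21.542865; 49 patients with eGFR >45, of whom 13 had a TNF Z-score above 0; Table 1 odds ratios 1.81 (MCP1) and 1.54 (TIMP1).

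**1. Reproduce the stated model.**
- exp(0.59214) = 1.81 and exp(0.4325066) = 1.54. The Table 1 odds ratios therefore match the output: the larger coefficient belongs to MCP1.
- Null log likelihood = 13 ln(13/49) + 36 ln(36/49) = -28.348. LR chi-square = 2 × (28.348 - 21.543) = 13.61 and pseudo R2 = 1 - 21.543/28.348 = 0.2401, both as stated.
- The only 2×2 table with 49 patients and 13 events that gives 75% and 82% has 6 true and 2 false positives: 6/8 = 75% and (6 + 34)/49 = 81.6%.

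**2. Can either verbal rule equal the model rule?** A probability of at least 50% means log odds ≥ 0. The log odds are a weighted sum, so a high value of one marker offsets a low value of the other. The pairs below (TIMP1/Cr, MCP1/Cr in ng/mg) test this without assuming any cut-off.

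| Pair | p, output coefficients | p, written equation |
|---|---|---|
| (16, 0.5) | 0.53 | 0.72 |
| (0.5, 16) | 0.72 | 0.53 |
| (0.5, 0.5) | 0.12 | 0.12 |
| (4, 0.5) | 0.33 | 0.44 |
| (0.5, 4) | 0.44 | 0.33 |
| (4, 4) | 0.74 | 0.74 |

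- *Both markers.* The model admits the first two pairs. To admit both, each cut-off must be at or below 0.5. The rule then also admits (0.5, 0.5), which the model refuses at 0.12.
- *Either marker.* The model refuses (4, 0.5) and (0.5, 4). To refuse both, each cut-off must lie above 4. The rule then also refuses (4, 4), which the model admits at 0.74.

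This holds with either coefficient assignment. For any common pair of finite cut-offs, the both-markers rule also selects a strict subset of the either-marker rule.

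**3. Does the coefficient exchange matter?**
- MCP1/Cr 8, TIMP1/Cr 0.5 (log2 values 3 and -1).
  - Output: -1.001269 + 0.59214×3 - 0.4325066 = 0.343, p = 0.58, eligible.
  - Written: -1.001269 - 0.59214 + 0.4325066×3 = -0.296, p = 0.43, not eligible.
- MCP1/Cr 1, TIMP1/Cr 4 (log2 values 0 and 2).
  - Output: -1.001269 + 0.4325066×2 = -0.136, p = 0.47, not eligible.
  - Written: -1.001269 + 0.59214×2 = 0.183, p = 0.55, eligible.
- Under the output, the boundary is MCP1/Cr 2^(1.001269/0.59214) = 3.23 at TIMP1/Cr 1, and TIMP1/Cr 2^(1.001269/0.4325066) = 4.98 at MCP1/Cr 1. Under the written equation these two values change places.

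**4. Illustration of size, on assumptions only.** Assume bivariate normal log2 markers with equal means and SDs, correlation 0.2 to 0.8, output coefficients, and one common cut-off placed on the model boundary. If the model selected 25% of those screened, the both-markers rule would select 11% to 18% and the either-marker rule 34% to 48%. The documents give neither a biomarker distribution nor cut-offs, so this shows only that the gap can be large.

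**The case against.** The best defence is that there is only one rule and the rest is shorthand. Protocol 2.2 says prospectively that its equations will be used for inclusion, and no other rule can be calculated. On that reading the defect is a missing cross-reference and loose and/or wording. This is plausible, and it may describe what was done. It does not remove the conflict, because the formal criteria in both documents differ from the text around them and nothing in them points to Protocol 2.2.

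Three stronger readings are tempting and are not supported.

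- *Wrong patients were enrolled, or sites applied the either-marker wording.* The documents do not say who judged criterion 3 or how. With at most 8 treated, all the rules may have agreed.
- *The 50% rule secures a 75% predictive value in the trial.* That figure rests on 6 of 8 flagged patients in the model's own fitting sample, all with eGFR >45, while the trial admits eGFR >30. Enrichment in the trial population is not established under any of the rules.
- *The anticipated 25% eligible share in Protocol 5.3 contradicts the model, which flags 8/49 = 16.3%.* The sample is too small and the eGFR limits differ too much to call that a contradiction.

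**Conclusion.** The point stands as an internal contradiction in the rule that defines the study population. The three statements cannot be made equivalent by any choice of single-marker cut-offs, provided the verbal rules are read as threshold rules on each marker. The one computable rule exists in two versions, and these give opposite eligibility for some marker pairs. The output and the Table 1 odds ratios agree with each other, and the written equation departs from both. How many screened or treated patients are affected cannot be determined from the documents. This should be corrected, but it does not show that the trial's selection went wrong.

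**What to change.** 1. Reconcile Protocol 2.2 first: check the written equation against the fitted model, the regression output and Table 1, and state one coefficient for each named marker.
2. Make criterion 3 (Protocol 5.1, SAP 5.2.1) refer to the sponsor's own rule, a predicted probability of TNF Z-score above 0 of at least 50% at screening, with the constant and each marker's coefficient written out. Pointing to the model or the table alone would carry the exchange into the criterion.
3. Align the protocol summary, Protocol 5.3 and SAP 5.1 with that criterion.
4. SAP 1.1 describes treatment in the past tense, so rewording may not change who was selected. The SAP should therefore state which rule and which coefficients were applied at screening, and add a listing of each treated participant's screening MCP1/Cr, TIMP1/Cr and predicted probability.
5. Where the 75% and 82% are cited, say that they come from the fitting sample with eGFR >45.

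The cost is the wording of one criterion and its repeats, a check of one equation, and one listing of at most 8 rows. The schedule already includes both markers at screening, so no new data are needed.
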